7.2. Treatment Compliance

Study treatment compliance (%) will be calculated as the actual number of vibegron doses taken divided by the expected number of vibegron doses, multiplied by 100 and summarized by treatment duration.

These numbers will be calculated as the sum of the number of tablets indicated as taken by the subject on each dispensation record. Where no treatment bottle is returned, and thus the actual number of doses taken is unknown, it will be assumed that the subject took medication as directed until another bottle was dispensed, their supply was exhausted, or end of treatment was noted. This is calculated as (minimum of [next dispensation date – dispensation date + 1], [doses dispensed] and [EOT date – dispensation date + 1]). Imputed values will be clearly noted in the listing.

The expected number of vibegron doses is the same as the calculated duration of exposure detailed in section 7.1.

Treatment Compliance will be summarized for the SAF-Ext and FAS-Ext population. Additionally, the number and percentage of subjects within each planned treatment duration with compliance in the following categories will be provided: <80%, 80 – 120%, and >120%. All data will be listed.

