6.1. Study Drugs Administered

Table 1 Summary of Study Drugs

Study Drug Name	Vibegron
Dosage Formulation	tablet
Identity of Formulation	75 mg
Route of Administration	oral
Dosing Instructions	once daily
Packaging and Labeling	Study drug will be provided in HDPE bottles with child-resistant caps. Each bottle will contain 32 tablets and will be labeled as required per country requirement.
Manufacturer	Patheon, Cincinnati, Ohio, US
Number and Timing of Drugs	Treatment Period: 1 tablet daily

The study drug will be supplied in bottles each containing 32 tablets (4-week treatment and 4-day extra supply) and labeled with the protocol number, lot number, expiration date, study drug name (vibegron 75 mg tablets) and number of tablets, directions for use, storage information, warning language (*Keep Out of Reach of Children. For Clinical Trial Use Only. To be used by qualified investigators only. Caution: New Drug—Limited by United States Law to Investigational Use.*), and the US Sponsor name and address. Immediately before dispensing the study drug, the investigator (or appropriately trained designee) will write the subject number, visit no. and the dispense date on the detachable panel of the label, which also includes the protocol number, bottle number and lot number.

Subjects will take 1 tablet of study drug (vibegron) once daily for up to 28 weeks.

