3.2. Violations and Deviation

Major protocol deviations are considered to have major impact on subject safety, efficacy or the validity of the study data.

Exclusion from per-protocol analysis is noted for each protocol deviation in the Protocol Deviation specifications. Patients with major protocol deviations that may impact efficacy results will be excluded from the PPS-Ext and PPS-Ext-I. Efficacy protocol deviations may include, but are not limited to the following:

- Subjects who do not meet the inclusion criteria
- Subjects who meet any of the exclusion criteria
- Concomitant use of prohibited medications
- Other (e.g., IP compliance < 70%)

Subjects excluded from the per protocol analysis in URO-901-3005 will also be excluded from per protocol analysis in URO-901-3006, with the exception of on-study protocol deviations in the placebo arm as noted in section 3.1.4.

The final list of major protocol deviations will be finalized and documented before database lock. All major protocol deviations related to efficacy will be discussed and finalized prior to database lock. Only major protocol deviations will be summarized and listed in the Clinical Study Report (CSR).

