7.1. Extent of Exposure

The duration of exposure with vibegron over studies URO-901-3005 and URO-901-3006 will be expressed as the time in days from the first dose of vibegron as recorded on the Study Drug Administration CRF page through to last treatment day (inclusive) as recorded on the End of Treatment CRF page, excluding any days where it is recorded that an interruption has occurred on the AE CRF page. If no last treatment date is recorded, it will be imputed as the minimum of the date of the last visit on study 3006 and the date when last dispensed study treatment was scheduled to be exhausted (last dispensation date + number of doses dispensed).

Interruptions to dosing can be due to delays in resupply (measured by gaps in the study drug log) or interruptions due to AE. Interruptions due to AE that overlap partially or completely will be listed separately but not double-counted for summing interruption days.

Gaps in the study drug log will be determined by comparing the dispensation date of a record to the previous dispensation date (where up to four bottles may have been dispensed). The gap is measured from the study day of previous dispensation + number of pills dispensed + number of days of AE interruption within the period.

$$\text{Interruption in days} = \text{date interruption started} - \text{date interruption stopped} + 1$$

This is given by the following formula:

$$\text{Duration (days)} = \text{date of last vibegron dose} - \text{date of first vibegron dose} - \text{interruption days} + 1$$

Duration of exposure will be summarized by treatment group and overall for the SAF-Ext set using summary statistics for continuous variables. A listing will present the treatment start and end date together with date(s) of interruption and the overall duration of exposure.

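### For unreturned supply, SAP 7.2 counts doses on days when drug was temporarily withheld, while expected doses leave those days out, so compliance is inflated for the men concerned

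*SAP*

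**What the plan says.** **Numerator (SAP 7.2).** Compliance is doses taken divided by expected doses, times 100. Doses taken normally come from tablet counts. Where nothing is returned, "it will be assumed that the subject took medication as directed until another bottle was dispensed", the supply ran out, or treatment ended. The count is then the "minimum of [next dispensation date – dispensation date + 1], [doses dispensed] and [EOT date – dispensation date + 1". Imputed values are to be marked in the listing.

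**Denominator (SAP 7.2 and 7.1).** "The expected number of vibegron doses is the same as the calculated duration of exposure detailed in section 7.1". That duration runs from first to last dose inclusive, "excluding any days where it is recorded that an interruption has occurred on the AE CRF page". The displayed formula for interruption days is printed as start minus stop plus 1, and the exposure formula subtracts the result.

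**Resupply gaps (SAP 7.1).** Before a gap between dispensings is declared, the rule adds to the tablets supplied the "number of days of AE interruption within the period".

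**Use.** SAP 7.2 tabulates compliance as below 80%, 80 to 120%, and above 120%. SAP 3.2 gives "Other (e.g., IP compliance < 70" per cent as an example of a deviation that may remove a man from the per-protocol sets.

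**The concern.** The two halves of the ratio cover different days. If drug was withheld for some days in an interval whose supply was never returned, those days enter the numerator as doses taken and are removed from the denominator. The resupply-gap rule in SAP 7.1 recognises that tablets are not used on withheld days. SAP 7.2 omits the same step, so the SAP is inconsistent with itself.

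Temporary holds are foreseen: Protocol 8.4.6.1 provides for withholding and conditional rechallenge, and SAP 7.3 plans a listing of adverse events that led to interruption. In a study whose primary objective is safety, a man whose drug was held could be tabulated as taking too many tablets. A man with poor adherence could also escape the lowest band or the per-protocol cut.

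**Working it through.** The documents state no compliance figure to reproduce, so the check applies SAP 7.1 and 7.2 as written to the protocol's visit days.

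**Inputs**
- Extension dispensing on Days 169, 197 and 253, and end of treatment (EOT) on Day 365 (Protocol 1.3 and 10.7).
- 32 tablets per bottle, one tablet daily (Protocol 6.1). Protocol Appendix 6 (10.5) gives a different dosing frequency. The two must be reconciled; the check uses 6.1 without judging which is right.
- Bottles at the three visits: 1, 2 and 4, that is 32, 64 and 128 tablets. This split is an assumption; SAP 7.1 allows up to four per dispensing. Supply is never the smallest term below.
- Interruption days are removed from the denominator, as the wording of SAP 7.1 says.

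**1. No interruption, nothing returned (28-week man).** The terms are 197 − 169 + 1 = 29, 253 − 197 + 1 = 57 and 365 − 253 + 1 = 113, which sum to 199. Exposure is 365 − 169 + 1 = 197 days. Compliance is 199/197 = 101.0%. The two extra doses are the two re-dispensing days, each counted twice.

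**2. The same man with k days withheld.** Compliance is 199/(197 − k), although he took every dose he was directed to take (true value 100%).

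| k | Reported compliance |
|---|---|
| 14 | 199/183 = 108.7% |
| 28 | 199/169 = 117.8% |
| 31 | 199/166 = 119.9% |
| 32 | 199/165 = 120.6% |

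**3. Early withdrawal after a hold.** Dispensing on Days 169 and 197, 14 days withheld (Days 205 to 218), EOT Day 230, nothing returned. Imputed doses are 29 + (230 − 197 + 1) = 29 + 34 = 63. Expected doses are 62 − 14 = 48. Compliance is 63/48 = 131%.

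**4. Masked low adherence.** 28 days withheld between Weeks 28 and 36, with that supply unreturned and the rest returned. He took 28 doses in the first interval, 56 − 28 = 28 in the second and 54 in the third. The true value is 110/169 = 65.1%. SAP 7.2 puts 57 in the second interval: 28 + 57 + 54 = 139, and 139/169 = 82.2%. This crosses both the 70% example and the 80% band. With 14 withheld days, a true 119/183 = 65.0% becomes 134/183 = 73.2%, which still crosses 70%.

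**5. Permanent stop.** As in step 3 but with no hold before the stop: 63/62 = 101.6%. The EOT term caps the count.

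**6. 52-week man, nothing returned.** The documents do not give the parent-study dispensing schedule. Assuming 1 to 6 dispensings before Week 24, imputed doses are 368 to 373. Exceeding 120% then needs 59 withheld days (368/306 = 120.3%) down to 55 (373/310 = 120.3%). Double counting alone gives 100.8% to 102.2%.

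**7. The printed interruption formula.** Taken literally, a 32-day hold gives −31 + 1 = −30 days. Subtracting −30 makes the denominator 197 + 30 = 227, and compliance is 199/227 = 87.7%. This contradicts the text of SAP 7.1, which excludes those days.

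**The case against.** Imputation is the exception. Tablet counts are the default, and Protocol 6.3 has sites try to recover all unused drug and empty bottles. Imputed values are marked in the listing, and interruption dates are listed with exposure. The phrase about taking medication as directed could be read as leaving out withheld days. Most men who stop drug stop for good: Protocol 7.2 withdraws them from the study, and the EOT term then limits the count. Urinary retention and a PVR volume of 300 mL or more lead to discontinuation under Protocol 7.1, so those safety cases do not produce the error. The study has no formal hypotheses, the per-protocol analysis is supportive, the 70% cut is only an example, and the band above 120% triggers nothing.

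Most of this stands and limits the size of the problem. It does not remove it. The formula that follows the as-directed phrase has no term for withheld days, and a flag in a listing corrects neither the summary table nor the per-protocol set.

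A reader might go further and infer that each unreturned bottle is imputed separately, so that four bottles count as 128 doses over a 113-day interval. The text points the other way. SAP 7.2 sums over dispensation records, and SAP 7.1 treats one dispensing as covering up to four bottles.

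**Conclusion.** The rule is wrong as written. For a man whose drug was temporarily withheld, who resumed, and whose supply for that interval was not returned, compliance is overstated by roughly the withheld days. The withheld-day mismatch drives the result; the doubled re-dispensing day adds about 1% in a 28-week man and cannot by itself lift anyone above 120% in these scenarios. Passing 120% takes about 32 withheld days in a 28-week completer with nothing returned, fewer after early withdrawal, and about 55 to 59 in a 52-week man.

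Two broader inferences are not supported. Men taken off drug for good are not shown as over-dosed (63/62 = 101.6%). Nor does every error in these two sections inflate compliance, since the reversed interruption formula, taken literally, lowers it.

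The figures rest on nominal visit days, one tablet daily, the assumed bottle split, and interruption days being removed as SAP 7.1 says in words. The documents give no frequency of holds or unreturned supply. Few men are likely to be affected, but the correction is cheap and worth making.

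**What to change.** In SAP 7.2, impute once per dispensation record, taking together all bottles dispensed at that visit, as the minimum of:
- next dispensation date − dispensation date − AE interruption days in the interval;
- doses dispensed, unreduced;
- EOT date − dispensation date + 1 − AE interruption days in the interval.

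Keep the flag for imputed values. In SAP 7.1, change the interruption formula to stop − start + 1, so that the denominator removes interruption days as its text says.

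Interruption days must come off the date terms only. Take 32 tablets, a next dispensing 50 days later and 18 days withheld: he was directed to take 32 doses and had 32 tablets. The form above gives min(50 − 18, 32) = 32. Subtracting after the minimum would give 32 − 18 = 14.

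With this form, the man in step 2 with 28 days withheld after Day 253 scores (28 + 56 + 85)/169 = 169/169 = 100%, and the masked case in step 4 returns to 110/169 = 65.1%.

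The cost is the imputation formula and its program, plus the one-line correction in SAP 7.1. No new data are needed. Some men's stated compliance becomes slightly lower.

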7.3. Adverse Events

AEs will be coded using MedDRA version 23.0 or higher.

All reported AEs (whether treatment emergent or not) on both study URO-901-3005 and URO-901-3006 will be included in by-subject AE listings on the Safety Set Extension. Sorting will be by country, site, subject, date of event, SOC, PT and then verbatim description. An additional overall AE listing will be presented for subjects that were enrolled but not dosed with vibegron on URO-901-3006.

An AE will be considered treatment emergent (TEAE) if it begins or worsens in severity after the first dose of vibegron on study URO-901-3005 or URO-901-3006 through 5 days after the last dose of vibegron. Partial AE start dates will be imputed as detailed in [Section 4.2.3](#).

Summary tables will be based on TEAEs. The incidence of TEAEs will be presented using counts and percentages of subjects with TEAEs and tabulated by SOC and PT. SOC will be sorted in descending frequency and PT within SOC will be sorted by descending frequency based on the incidence across subjects overall. If a subject has multiple occurrences (start and stop) of an event associated with a specific SOC or PT within a SOC, a subject will only be counted once in the incidence count for the SOC or PT within SOC respectively.

An overall summary table of AEs will be presented detailing the number and percentage of subjects, and number of events for the following categories:

- At least one TEAE;

- At least one Treatment-Related TEAE;
- At least one Grade ≥ 3 TEAE (Mild = Grade 1, Moderate = Grade 2, Severe of Medically Significant = Grade 3, Life-Threatening = Grade 4, Death = Grade 5)
- At least one Grade ≥ 3 Treatment-Related TEAE;
- At least one Serious TEAE;
- At least one Serious Treatment-Related TEAE;
- At least one TEAE leading to Discontinuation from Study Medication;
- At least one TEAE of Special Interest;
- At least one Treatment-Related TEAE of Special Interest

Where not otherwise noted, all the following summaries are presented by PT:

- All TEAEs (by SOC and PT);
- Treatment-Related TEAEs (i.e., possibly or probably related);
- TEAEs occurring in 2% or more of the population;
- All TEAEs by SOC, PT, and maximum severity (where the maximum intensity per patient will be counted at each level of summarization);
- TEAEs with Grade ≥ 3 ;
- Treatment-Related TEAEs with Grade ≥ 3 ;
- Serious TEAEs;
- Treatment-Related Serious TEAEs;
- Fatal TEAEs;
- TEAEs leading to Discontinuation from Study Treatment;
- TEAE of Special Interest (by protocol-defined AESI category);
- Treatment-Related TEAE of Special Interest (by protocol-defined AESI category);
- Non-fatal TEAEs;
- Hypertension TEAEs by Pre-existing Hypertension (Yes vs No) and Baseline Hypertension (Yes vs. No). Hypertension TEAEs will be selected as any TEAE with a preferred term of Hypertension.

In addition, a summary of all TEAEs by PT occurring in at least 2% of subjects will be created and ordered by descending overall frequency.

Adverse events of special interest for this study include:

- Adverse events consistent with urinary retention
- Adverse events suggestive of cystitis or urinary tract infection (UTI)
- Potential major cardiac and cerebrovascular events, including death (or any event with fatal outcome), myocardial infarction, cerebrovascular accident, hospitalization for unstable angina or chest pain, hospitalization for heart failure requiring hospitalization, and coronary revascularization/angioplasty/stent
- Adverse events consistent with hypertension (see protocol section 8.4.6)
- Adverse events consistent with orthostatic hypotension as confirmed by orthostatic vital signs
- Elevated serum aspartate aminotransferase (AST) or alanine aminotransferase (ALT) lab value requiring that study drug be temporarily withheld or permanently discontinued
- Neoplasms

Treatment listings will include the planned treatment duration, start and stop dates/times of the AE, study day (relative to start of double-blind treatment on URO-901-3005) and treatment day (relative to the day of first dose of vibegron). A treatment related AE is defined as an AE for which the investigator classifies the AE as being “Probably Related” or “Possibly Related” to study treatment on the Adverse Event CRF. Missing relationship and severity (intensity) will be imputed per Section 4.2.3.

The following additional listings will be provided:

- Listing of Deaths
- Listing of Serious TEAEs
- Listing of Treatment-Emergent AESIs
- Listing of TEAEs Leading to Withdrawal or Interruption of Study Treatment
- Listing of all AEs with a flag for TEAEs and onset (Prior = prior to first dose of vibegron or Treatment = on or after first dose of vibegron.)
- Listing of all medical history including pre-treatment adverse events with coded preferred terms in the hypertension AE search list:
 - Accelerated hypertension
 - Diastolic hypertension
 - Essential hypertension
 - Hypertension

- Hypertensive crisis
- Hypertensive emergency
- Hypertensive heart disease
- Malignant hypertension
- Malignant hypertensive heart disease
- Secondary hypertension
- Supine hypertension
- Systolic hypertension.

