1.2. Study Design

1.2.1. Overall Study Design

This is an international Phase 3, open-label 28-week extension study to evaluate the safety and efficacy of vibegron 75 mg in men with symptoms of OAB on stable doses of pharmacological therapy for BPH. This study is an extension for subjects who have completed the Phase 3, double-blind, randomized, 24-week Study URO-901-3005.

Approximately 300 men with symptoms of OAB on stable doses of pharmacological therapy for BPH who completed 24 weeks in Study URO-901-3005 and continue to qualify for this study may be permitted to enroll in this extension study, from approximately 60 study sites.

During this extension study, subjects who had been randomized in Study URO-901-3005 to receive vibegron 75 mg will continue their same treatment once daily for an additional 28 weeks, and subjects who had been randomized in Study URO-901-3005 to the placebo group will receive study treatment of vibegron 75 mg once daily for 28 weeks during the extension. Thus, through participation in both the URO-901-3005 and URO-901-3006 (extension) studies, subjects originally randomized to vibegron will receive 52 weeks total of vibegron treatment, and subjects originally randomized to placebo will receive 28 weeks total of vibegron treatment.

[figure not shown]
Study visits will be named to reflect continuation from Study URO-901-3005, with the first study visit of this extension study occurring at Week 24. Following enrollment in this extension study, subjects will return to the clinic for visits at Week 28, Week 36, and Week 52 (all relative to Day 1 of Study URO-901-3005). A telephone contact will occur at Week 44 to review AEs/serious AEs (SAEs) and concomitant medications.

This study consists of a 28-week open-label Treatment Period. Unscheduled Visit(s) may be arranged as needed.

A Data Safety Monitoring Board (DSMB) will be retained to assess, on an ongoing basis, all safety aspects of this study. This will be an external independent DSMB that monitors the safety for both Study URO-901-3005 and Study URO-901-3006. The detailed activities including meeting plans will be described and documented in the DSMB Charter. A separate statistical analysis plan will be prepared for the DSMB.

The study schema is shown in [Figure 1](#).

Figure 1: Study Schema

*Week 44 consists of a telephone contact to review AEs/SAEs and concomitant medications; no clinic visit is required at that timepoint.

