3.1.2. Safety Analysis Set Extension

The Safety Analysis Set Extension (SAF-Ext) will serve as the primary population for the analysis of safety data in this trial.

The SAF-Ext consists of all randomized subjects in Study URO-901-3005 who

- a) have completed the 24-week treatment period in the Study URO-901-3005, and
- b) enrolled into the extension Study URO-901-3006 and received at least one dose of vibegron in this study.

Safety endpoints will be descriptively summarized for the entire Safety Analysis Set Extension. No imputation will be performed for missing safety data. Baseline will be established as the last observation prior to the first dose of vibegron. All safety data collected on or after the first exposure to vibegron within the combined experience of the patient on URO-901-3005 and

URO-901-3006 will be included in the safety analysis for URO-901-3006, and all analyses by visit will index visits from the first dose of vibegron on either study; subjects who received placebo in study URO-901-3005 will only contribute safety data up to Week 28.

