4.2. General Data Handling Conventions

4.2.1. Study Treatment Description

Treatment groups based on the randomized treatment in the parent study will be displayed as shown in the following table:

Table 1: Study Treatment Description

Data Displays for Reporting		
Description	Sections Included	Order in TLF
52 weeks Vibegron 75mg	Demographic and baseline data, Efficacy, Safety	1

28 weeks Vibegron 75mg	Demographic and baseline data, Efficacy (descriptive tables only), Safety	2
Overall Vibegron 75 mg	Demographic and baseline data, Safety	3

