4.2.2. Reporting Conventions

General rules

In general, all collected safety data and any derived efficacy and PRO data will be presented in subject data listings for all enrolled subjects. This includes all data collected on the parent study, URO-901-3005, relevant to the definition of baseline and all data collected on URO-901-3005 after the first dose of vibegron, excluding assessments not repeated during 3006 (orthostatic vital signs, ECGs, urodynamics, and prostate volume measurement). Listings will be ordered by treatment group, subject number, and assessment week or event date. The treatment group presented in listings will be based on the actual treatment assignment in study URO-901-3005 (placebo as 28 Weeks Vibegron 75mg, vibegron 75mg as 52 weeks Vibegron 75mg), unless otherwise noted.

Summary tables will be provided for all subjects who sign informed consent for study URO-901-3006. Unless otherwise specified; all demographic and baseline data and safety data will be presented by treatment group and overall. Unless otherwise specified; all efficacy data will be presented by treatment group. In general, continuous variables will be summarized to indicate the population sample size (N), number of subjects with available data (n), arithmetic mean, SD, median, minimum, Q1, Q3 and maximum values. Categorical variables will be summarized by the population size (N), number of subjects with available data (n), number of subjects in each category, and the percentage of subjects in each category. Unless otherwise noted, the denominator to determine the percentage of subjects in each category will be based on the number of subjects with available data (n) in the analysis set of interest. Select ordinal data may be summarized using both descriptive statistics and counts and percentages of subjects in each category, as appropriate.

The data analyses will be conducted using the SAS[®] System (SAS Institute Inc., Cary, NC) version 9.4 or above. The eClinical Solutions standard operating procedures will be followed for the validation of all SAS programs and outputs.

Formats

Numeric data will be reported at the precision collected on the eCRF. The reported precision from non eCRF sources may be adjusted to a clinically interpretable number of decimal places.

Unscheduled Visits

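### TEAE percentages are not adjusted for time at risk, and the Overall column mixes 28-week and 52-week exposure, so it corresponds to neither a 28-week nor a one-year risk

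*SAP*

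**What the plan says.** SAP 7.3 sets the measure: "The incidence of TEAEs will be presented using counts and percentages of subjects with TEAEs and tabulated by SOC and PT". A subject counts once per SOC or PT. The overview table is described as "detailing the number and percentage of subjects, and number of events for the following categories", and nine categories follow. Under SAP 4.2.2 the default denominator for percentages is "based on the number of subjects with available data (n) in the analysis set of interest", which is a number of subjects and not person-time.

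SAP 4.2.2 also says that, unless otherwise specified, "all demographic and baseline data and safety data will be presented by treatment group and overall". Table 1 in SAP 4.2.1 therefore gives safety displays three columns: the 52-week group, the 28-week group and "Overall Vibegron 75 mg". SAP 1.2.1 explains the longer duration: "subjects originally randomized to vibegron will receive 52 weeks total of vibegron treatment". The men from the parent placebo arm, who start vibegron only at extension entry, have 28 weeks in total. SAP 3.1.2 adds that "subjects who received placebo in study URO-901-3005 will only contribute safety data up to Week 28", with visits indexed from the first vibegron dose.

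No person-year rate, Kaplan-Meier or cumulative-incidence estimate, or adverse-event display by time interval appears in SAP 7.3 or in the lists of output tables and figures (SAP Tables 9 and 10). SAP 7.1 summarises days of exposure by group and overall, but these are not used as a denominator for adverse events.

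**The concern.** Long-term safety is the primary objective and the study is descriptive, so the adverse-event tables are its main result. A percentage of subjects reads as a risk only if the reader knows over what period. Planned vibegron exposure differs almost two-fold between the groups (52/28 = 1.86), and about a third of subjects are expected to drop out. The Overall percentage averages risks over two different periods, with weights set by how many men rolled over from each parent arm. Overall frequency also sets the sort order of the SOC and PT tables and of the table of TEAEs at or above 2%. A reader looking for the long-term incidence of an event would find no period to attach to that figure.

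**Working it through.** **1. The plan's own figure.** SAP 1.2.4 gives about 300 subjects, about 33% dropout and 100 completing one year on vibegron. The split by parent arm is not stated. With 1:1, 300 × 0.5 × (1 − 0.33) = 100.5, which reproduces the 100. The 1:1 split is therefore an assumption, but one consistent with the SAP's arithmetic.

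**2. Planned exposure.** With 150 men per group and no dropout: 150 × 52/52 + 150 × 28/52 = 150 + 80.8 = 230.8 patient-years. The mean is (52 + 28)/2 = 40 weeks, which is neither horizon.

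**3. Constant hazard, no dropout.** The documents give no event risks, so these are illustrative. For a true 52-week risk p:

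- λ = −ln(1 − p)/52 per week
- 28-week risk = 1 − exp(−28λ)
- Overall = mean of the two

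For p = 0.10: λ = 0.002026; 28-week risk = 1 − exp(−0.0567) = 0.0552; Overall = (0.1000 + 0.0552)/2 = 0.0776.

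**4. Adding 33% dropout.** Assume exponential dropout unrelated to the event: δ = −ln(0.67)/28 = 0.01430 per week over the 28 extension weeks, and none in the first 24 weeks of the 52-week group, since the safety set contains only parent completers. The 5-day TEAE tail is ignored.

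- 28-week column = λ/(λ + δ) × [1 − exp(−28(λ + δ))]
- 52-week column = 1 − exp(−24λ) + exp(−24λ) × (28-week column)

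For p = 0.10: 28-week column = 0.1241 × 0.3670 = 0.0455; 52-week column = 0.0475 + 0.9525 × 0.0455 = 0.0908; Overall = 0.0682. That is 32% below the one-year risk and 24% above the 28-week risk.

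| True 52-week risk | True 28-week risk | Overall, no dropout | Overall, 33% dropout |
|---|---|---|---|
| 2% | 1.1% | 1.5% | 1.35% |
| 5% | 2.7% | 3.9% | 3.4% |
| 10% | 5.5% | 7.8% | 6.8% |
| 20% | 11.3% | 15.7% | 13.8% |

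An event with a 2% one-year risk would fall below the 2% display threshold if that threshold is applied to the Overall column.

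**5. Sensitivity.** With 40% to 60% of subjects in the 52-week group, 0% to 33% dropout and one-year risks of 2% to 40%, Overall lies 16% to 37% below the one-year risk and 11% to 51% above the 28-week risk.

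**6. Shape of the hazard.** If a 10% risk falls entirely at Week 4 and nobody drops out, both columns and Overall show 10% and there is no gap. If it falls entirely after Week 28, the columns show 10% and 0%, and Overall shows 5%.

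**7. What a rate recovers.** Under a constant hazard, subjects with a first event divided by time at risk returns the true rate. For p = 0.10 with 33% dropout, mean time at risk is 44.8 weeks (52-week group) and 22.5 weeks (28-week group). The rates are 0.0908 × 52/44.8 and 0.0455 × 52/22.5, both about 10.5 per 100 patient-years. The rate stays at 10.5 across the splits and dropout levels tested, while Overall moves between 6.4% and 8.2%. Without a constant hazard this agreement is lost: in the Week 4 case the rates are 0.10 × 52/25.6 = 20.3 per 100 patient-years in the 28-week group and 0.10 × 52/47.2 = 11.0 in the 52-week group.

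**8. Where a simple rate goes wrong.** SAP 3.1.2 admits only men who completed the 24-week parent period, and Protocol 5.2 (exclusion 1) removes men with a parent-study SAE judged possibly or probably related. In the 52-week group such events cannot appear in the first 24 weeks. Take a 10% discontinuation risk over the 28 extension weeks in both groups: λ = −ln(0.9)/28 = 0.003763 per week, and time at risk in the extension is 0.10/0.003763 = 26.6 weeks.

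- 28-week group: 0.10 × 52/26.6 = 19.6 per 100 patient-years
- 52-week group, counting all vibegron time: 0.10 × 52/(24 + 26.6) = 10.3 per 100 patient-years

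An equal hazard looks halved. Counting from the first extension dose gives 19.6 in both groups.

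**The case against.** The strongest reply is that the two quantities a reader wants are already planned. The 52-week column comes first and the 28-week column second, each labelled with its planned duration. Without dropout they show the correct risks (10% and 5.5% in the example). That stands, and it confines the main problem to the third column. With 33% dropout the separate columns show 9.1% and 4.6%, so they are crude but much closer.

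A reader might infer that Overall is the headline result and understates one-year risk. The documents do not support that. Nothing in the SAP presents Overall as a one-year risk, the Protocol synopsis frames the objective as dosing for up to 52 weeks, and Protocol 9.3.2 specifies the pooling in advance. Any shortfall also depends on the unknown shape of the hazard.

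A reader might also infer that the plan rests on a group comparison that cannot be interpreted. No such comparison is planned: SAP 1.2.3 has no hypotheses and SAP 7 excludes inferential testing of safety data.

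Nor are percentages all that is shown. Event counts in the overview table, set against exposure in SAP 7.1, allow a rough event rate for those nine categories. First-event rates by AESI category or PT cannot be obtained that way.

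Finally, rates are not neutral. They are equal across groups only under a constant hazard, and completer selection distorts them for some events. Both points stand and shape the fix.

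**Conclusion.** The point holds for the Overall column and, to a lesser degree, for the unadjusted percentages in the two group columns. With a constant hazard, a 1:1 split and non-informative dropout, all of which are assumptions, a 10% one-year risk (5.5% at 28 weeks) appears in Overall as 7.8%, or about 6.8% with the SAP's 33% dropout. For early-clustered events the gap is small; for late events it is larger. The plan contains no error in the group columns as such, and makes no claim that Overall estimates one-year risk. What is missing is a time-adjusted measure and a label saying what Overall mixes. This merits a change before the tables are produced, but it does not invalidate the planned displays.

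**What to change.** In the adverse-event tables already planned:

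- Label the Overall percentage as mixed 28/52-week exposure.
- Add exposure-adjusted incidence rates (subjects with a first event per 100 patient-years at risk), by group and overall, for all TEAEs, serious TEAEs and each AESI category.
- For events that prevent entry to the extension (TEAEs leading to discontinuation, related SAEs, and AESIs that force withdrawal), count events and time at risk from the first extension dose in both groups.
- If a display of Weeks 0-28 on vibegron is produced, footnote that the first 24 weeks of the 52-week group are conditional on parent completion.

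No new data are needed: dose dates, exposure and treatment day are already derived (SAP 4.3.3, 7.1 and 7.3). The cost is a few added columns, plus programming of time to first event per category. The rates summarise risk well only where the hazard is roughly constant, so the group percentages should stay beside them.
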